18.0 Records and Data Collection Procedures

Submission Timetable

Initial Material(s) -

| Case Report Form (CRF) | Active-Monitoring Phase (Compliance with Test Schedule Section 4.0) |
|--------------------------------------|---|
| On-Study Form | |
| Baseline Adverse Event Form | |
| Pretreatment Measurement Form | |
| | |
| Baseline Research Tissue Submission | $\Box 2$ weeks after registration |
| Form (see Section 17.0) | |
| Baseline Concomitant Medication Form | |
| | |
| End of Active Treatment/Cancel | Submit □2 weeks after registration if |
| Notification Form | withdrawal/refusal occurs prior to beginning |
| | protocol therapy |

Test Schedule Material(s) -

| CRF | Active-Monitoring Phase (Compliance with Test Schedule Section 4.0) | | | | |
|---------------------------------|---|---------------------|--|--|--|
| | At each evaluation during treatment | At end of treatment | | | |
| Evaluation/Treatment Form | \mathbf{Y}^2 | X | | | |
| Adverse Event Form | X | X | | | |
| Measurement Form | \mathbf{Y}^{1} | \mathbf{Y}^1 | | | |
| Research Tissue Submission Form | X (see Section 17.0) | V | | | |
| Concomitant Medication Form | X | X | | | |
| End of Active Treatment/Cancel | | X | | | |

| CRF | Active-Monitoring Phase (Compliance with Test Schedule Section 4.0) | | | | |
|---|---|---------------------|--|--|--|
| | At each evaluation during treatment | At end of treatment | | | |
| Notification Form | | | | | |
| Notification Form – Grade 4 or 5 Non-AER Reportable Events/Hospitalization Form | At each occurrence (see Section 10.0) | | | | |
| ADR/AER | At each occurrence (see Section 10.0) | | | | |

- 1. Submit supporting documentation of response or progression to the MCCC operations office via RAVE.
- 2. Complete at each evaluation during Active Treatment (see Section 4.0).

Follow-up Material(s) -

| 1 onow-up material(s) | | | | | |
|-----------------------|---|--------------------|--------------------------|-----------|--------------------|
| | | Ev | ent Monit | toring Pl | hase ¹ |
| CRF | q. 3 months until PD ² | At PD ² | After PD q. 6 mos. | Death | New Primary |
| Event Monitoring Form | X | X | X | X | At each occurrence |

- 1. If a patient is still alive 2 years after registration, no further follow-up is required.
- 2. Submit supporting documentation of response or progression to the MCCC operations office via RAVE.

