11.0 Treatment Evaluation Using RECIST Guideline

NOTE: This study uses protocol RECIST v1.1 template dated 2/16/2011. See the footnote for the table regarding measureable disease in Section 11.44, as it pertains to data collection and analysis.

Response and progression will be evaluated in this study using the new international criteria proposed by the revised Response Evaluation Criteria in Solid Tumors (RECIST) guidelines (version 1.1) Changes in the largest diameter (unidimensional measurement) of the tumor lesions and the short axis measurements in the case of lymph nodes are used in the RECIST guideline.

- 11.1 Schedule of Evaluations: For the purposes of this study, patients should be reevaluated every 8 weeks.
- 11.2 Definitions of Measurable and Non-Measurable Disease
 - 11.21 Measurable Disease
 - 11.211 A non-nodal lesion is considered measurable if its longest diameter can be accurately measured as □2.0 cm with chest x-ray, or as ≥1.0 cm with CT scan, CT component of a PET/CT, or MRI.

 Tumor lesions in a previously irradiated area are considered measurable disease under the following conditions:
 - a. The radiation completion date is \geq 90 days from the registration date.
 - b. There is objective evidence of disease progression after completion of the radiation therapy.
 - 11.212 A superficial non-nodal lesion is measurable if its longest diameter is ≥ 1.0 cm in diameter as assessed using calipers (e.g. skin nodules) or imaging. In the case of skin lesions, documentation by color photography, including a ruler to estimate the size of the lesion, is recommended.

- 11.213 A malignant lymph node is considered measurable if its short axis is \geq 1.5 cm when assessed by CT scan (CT scan slice thickness recommended to be no greater than 5 mm).
- 11.214 Clinical Lesions: Clinical lesions will only be considered measurable when they are superficial (e.g. skin nodules and palpable lymph nodes) and >1.0 cm diameter as assessed using calipers (e.g. skin nodules). In the case of skin lesions, documentation by color photography, including a ruler to estimate the size of the lesion, is recommended.

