13.0 Treatment/Follow-up Decision at Evaluation of Patient

- 13.1 Patients who are CR, PR, or SD will continue treatment per protocol.
- Patients who develop PD while receiving therapy will go to the event-monitoring phase.
- Patients who go off protocol treatment for reasons other than PD will go to the event-monitoring phase per Section 18.0.

- 13.4 Patients who develop PD in the CNS only should receive resection and/or brain radiationand continue treatment on study after completion of CNS treatment.
- Patients who develop non-CNS PD at any time should go to event monitoring. These patients should be treated with alternative chemotherapy if their clinical status is good enough to allow further therapy.
- 13.6 A patient is deemed *ineligible* if after registration, it is determined that at the time of registration, the patient did not satisfy each and every eligibility criteria for study entry. The patient may continue treatment off-protocol at the discretion of the physician as long as there are no safety concerns, and the patient was properly registered. The patient will go directly to the event-monitoring phase of the study (or off study, if applicable).
 - If the patient received treatment, all data up until the point of confirmation of ineligibility must be submitted. Event monitoring will be required per Section
 - 18.0 of the protocol.
 - If the patient never received treatment, on-study material must be submitted. Event monitoring will be required per Section 18.0 of the protocol.
- 13.7 A patient is deemed a *major violation*, if protocol requirements regarding treatment in cycle 1 of the initial therapy are severely violated that evaluability for primary end point is questionable. All data up until the point of confirmation of a major violation must be submitted. The patient will go directly to the event-monitoring phase of the study. The patient may continue treatment off-protocol at the discretion of the physician as long as there are no safety concerns, and the patient was properly registered. Event monitoring will be required per Section 18.0 of the protocol.
- 13. 8 A patient is deemed a *cancel* if he/she is removed from the study for any reason before any study treatment is given. On-study material and the End of Active Treatment/Cancel Notification Form must be submitted. No further data submission is necessary.

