16.3 Phase II Design and Analysis

16.31 Primary Endpoint: The primary endpoint of this trial is the 4-month progression-free survival rate. Throughout Section 16.0, "4-month progression-free survivor" will be considered synonymous with "success", unless otherwise specified. A patient is considered to be a 4-month progression-free survivor if the patient is 4 months from registration without a documentation of disease progression (note, the patient need not be on study treatment at 4 months to be considered a success). All patients meeting the eligibility criteria who have signed a consent form and have initiated treatment will be evaluable for the primary endpoint.

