16.4 Statistical Design

16.41 Decision Rule: The largest success proportion where the proposed treatment regimen would be considered ineffective in this population is 35%, and the smallest success proportion that would warrant subsequent studies with the proposed regimen in this patient population is 55%. The following one-stage design based on properties of the binomial distribution uses 37 patients to test the null hypothesis that the true success proportion in a given patient population is at most 35%.

The null 4-month progression-free survival rate of 35% is based on Figure

2 of Scagliotti et al (2008). In the subgroup of patients with squamous cell carcinoma on the cisplatin / gemcitabine arm, approximately 65% of patients were progression-free 4 months after randomization (i.e., at or near completion of first-line therapy). Four months subsequent to this time point, the PFS rate was approximately 25%. Thus, among those who were progression-free at or near completion of first-line therapy, the subsequent 4-month PFS rate for patients receiving no maintenance therapy following first-line cisplatin / gemcitabine is approximately 35% ($\approx 0.25/0.65$).

Enter 37 patients into the study. If 16 or fewer successes are observed in the first 37 evaluable patients, we may consider this regimen ineffective in this patient population. If 17 or more successes are observed in the first 37 evaluable patients, we may recommend further testing of this regimen in subsequent studies in this population.

- 16.411 Over Accrual: If more than the target number of patients are accrued, the additional patients will not be used to evaluate the stopping rule or used in any decision making process. Analyses involving over accrued patients is discussed in Section 16.34.
- 16.42 Power and Significance Level: Assuming that the number of successes is binomially distributed, the significance level is ≤0.12 and the probability of declaring that this regimen warrants further studies (i.e., statistical power) under various success proportions can be tabulated as a function of the true success proportion as shown in the following table.

| If the true success proportion is | 0.35 | 0.40 | 0.45 | 0.50 | 0.55 |
|--|------|------|------|------|------|
| then the probability of declaring that the regimen warrants further studies is | 0.11 | 0.28 | 0.52 | 0.74 | 0.90 |

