16.52 Definitions and Analyses of Secondary, Exploratory, and Correlative Endpoints

Survival time is defined as the time from registration to death due to any cause. The distribution of survival time will be estimated using the method of Kaplan-Meier (1958).

Progression-free survival time is defined as the time from registration to the earliest date of documentation of disease progression. If a patient dies without a documentation of disease progression the patient will be considered to have had disease progression at the time of their death. In the case of a patient starting treatment and then never returning for any evaluations, the patient will be censored for progression 1 day post-registration. The distribution of progression-free survival time will be estimated using the method of Kaplan-Meier (1958).

A response is defined to be either a CR or PR noted as the objective status. As response rate is a secondary endpoint, confirmation is no longer required per RECIST v1.1. The overall response rate will be estimated in the subset of patients with measureable disease by the number of responses in evaluable patients with measurable disease divided by the total number of evaluable patients with measureable disease. The appropriate confidence interval will be calculated based on the binomial distribution.

Duration of response is defined for all evaluable patients with measurable disease who have achieved a response as the date at which the patient's earliest best objective status is first noted to be either a CR or PR to the earliest date progression is documented. If a patient dies subsequent to the response without a documentation of disease progression, the patient will be considered to have had disease progression at the time of their death. In the case of a patient failing to return for evaluations before a documentation of disease progression, the patient will be censored for progression on day 1 post response or the date of last evaluation (whichever one occurs later). The distribution of

duration of response will be estimated using the method of Kaplan-Meier (1958).

Translational analyses: Given the small sample size, all translational analyses are considered exploratory and no adjustment for multiplicity will be employed. One-sided p-values

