evidence of a linear association, and also as a binary categorical variable based on the sample median IHC score for the given marker. Given availability of information regarding PFS beyond the time point of interest of 4 months, in exploratory analyses, associations of the aforementioned predictor variables with PFS at any time point will be evaluated using the Kaplan-Meier method and Cox proportional hazards models (censoring at the date of last follow-up), which will account for the varying lengths of follow-up between patients. Diagnostic Slides from Original and /or Recurrent Tissue.

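### No tumor scan is scheduled for patients who stop treatment without progression, yet 16.31 counts them as 4-month successes unless progression has been documented

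*Combined protocol and SAP*

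**What the plan says.** - **Evaluation interval.** Section 11.1 says that "patients should be reevaluated every 8 weeks", with no restriction to time on treatment.
- **Test schedule.** Section 4.0, footnote 2, attaches tumor assessment to treatment cycles (after Cycles 2, 4, 6 and so on).
- **Stopping without progression.** Section 13.3: "Patients who go off protocol treatment for reasons other than PD will go to the event-monitoring phase per Section 18.0".
- **Event monitoring.** In Section 18.0 the only item for this phase is the Event Monitoring Form, due "q. 3 months until PD". The Measurement Form is listed during treatment and at end of treatment, not afterwards. Footnote 2 asks for supporting documents when a response or progression is reported.
- **Primary endpoint.** Section 16.31 defines success as being 4 months from registration with no progression documented, and adds that "the patient need not be on study treatment at 4 months to be considered a success". It does not require a scan.
- **Censoring.** For PFS, Section 16.52 gives a censoring date only for patients who never return (day 1). For duration of response it uses day 1 after response or "the date of last evaluation (whichever one occurs later"). The exploratory marker analyses in 17.3 specify "censoring at the date of last follow-up".

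**The concern.** How closely progression is looked for depends on whether the patient is still taking study drug. Patients who leave treatment for toxicity or refusal have the least scheduled assessment, yet they stay in the denominator and are scored as successes by default.

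This is a foreseeable group. Section 8.2 sends patients to event monitoring for several toxicities, including interstitial pneumonitis of any grade, high-grade lipid elevations and some toxicities that persist beyond 14 days. The error runs in one direction: a missed progression can only add a success. It also grows with the number of patients who stop for toxicity, so a poorly tolerated regimen could look more active than it is. In a single-arm trial with a fixed cut-off, no control group shares the error.

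**Working it through.** **1. Reproduce the design.** Section 16.41 takes 35% as the null rate and 55% as the rate of interest. The rule is at least 17 successes in 37. The exact binomial P(X ≥ 17 | 37, p) is:

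| p | 0.35 | 0.40 | 0.45 | 0.50 | 0.55 |
|---|---|---|---|---|---|
| Computed | 0.112 | 0.282 | 0.518 | 0.744 | 0.898 |
| Section 16.42 | 0.11 | 0.28 | 0.52 | 0.74 | 0.90 |

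The plan's figures reproduce. They hold if every patient's 4-month status is known correctly.

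**2. Locate the unscanned window.** At 30.4375 days per month, 4 months is 4 × 30.4375 / 7 = 17.4 weeks. An 8-weekly schedule gives scans at weeks 8 and 16. A patient who stops just after the week-8 scan has no explicitly scheduled scan between then and 4 months under 4.0 and 18.0.

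**3. Risk in that window.** Assume exponential PFS with a 4-month rate of 35%. For a patient progression-free at t months, the chance of progressing before month 4 is r = 1 − 0.35^((4 − t)/4).

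- Week 8 (t = 56/30.4375 = 1.84): r = 0.433
- Week 4 (t = 28/30.4375 = 0.92): r = 0.554

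**4. Effect on the false-positive probability.** Let q be the share of all patients who stop at that time without progression, and m the share of their later pre-4-month progressions that go undocumented. The apparent null rate is 0.35 + q × r × m. The documents give neither q nor m. The table assumes q = 5%, 15% or 25% and m = 0.5.

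| q | Stop at week 8: apparent rate | P(≥17/37) | Stop at week 4: apparent rate | P(≥17/37) |
|---|---|---|---|---|
| 0% | 0.350 | 0.112 | 0.350 | 0.112 |
| 5% | 0.361 | 0.141 | 0.364 | 0.150 |
| 15% | 0.382 | 0.212 | 0.392 | 0.247 |
| 25% | 0.404 | 0.300 | 0.419 | 0.369 |

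Example: 0.35 + 0.15 × 0.433 × 0.5 = 0.382.

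**5. The same in patients.** An average of one misclassified progressor in 37 gives an apparent rate of 0.35 + 1/37 = 0.377 and P = 0.193. Two give 0.404 and 0.299. Section 16.42 states a limit of 0.12.

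**The case against.** The strongest reply is that Section 18.0 is a timetable for submitting forms, not a test schedule, and that the 8-weekly rule in 11.1 already covers patients off treatment. There are also partial safeguards:

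- The Measurement Form is listed at end of treatment, so tumor status at stopping is to be reported.
- Section 11.45 classes symptomatic deterioration that forces discontinuation as progression, and asks for efforts to document objective progression afterwards.
- Section 16.52 counts death as progression in PFS and censors patients who never return at day 1.
- Section 16.512 adds a Kaplan-Meier estimate when patients are lost before 4 months.

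Much of this stands. It limits the exposed group to living patients who stopped without progression and remain in contact. It does not close the gap, because nothing makes a scan a condition of success, and a site following 4.0 and 18.0 would not schedule one.

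A reader might draw three stronger conclusions that the documents do not support:

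- **That off-treatment patients are not imaged at all.** The documents show only that no scan is scheduled in event monitoring. Scans in routine care may occur.
- **That the last-follow-up rule in 17.3 inflates the success count.** That rule governs exploratory marker analyses. The primary endpoint is a binary proportion, and the PFS curve in 16.52 has no general censoring date stated.
- **That the false-positive probability reaches 0.157, 0.277 or 0.426 for q = 5%, 15% or 25%.** Those values come from 0.35 + q × 0.65 × 0.5, which applies the full risk from registration to patients who were progression-free when they stopped. They hold only if all of them stop at registration.

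**Conclusion.** The concern holds for the primary endpoint through 4.0, 11.1, 13.3, 16.31 and 18.0 taken together. As written, the plan lets a patient with unimaged progression count as a success, and the resulting bias is upward.

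The true size is unknown. Under the stated assumptions (exponential PFS, half of the later progressions undocumented, 5% to 25% stopping), the false-positive probability at a true 35% is 0.141 to 0.300 for stopping at week 8 and 0.150 to 0.369 for stopping at week 4, against 0.112 as designed. The design has little room for this error, since an average of one misclassified patient takes it past the stated 0.12. If routine care images these patients on much the same interval, the effect could be small.

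The PFS censoring wording is a secondary matter. It affects the PFS curves and the marker analyses, not the go/no-go decision.

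**What to change.** 1. **Assessment schedule (4.0, 11.1, 13.3, 18.0).** Reconcile these sections so that patients off treatment without progression keep the 8-weekly tumor evaluation of 11.1 until progression, death or withdrawal, and at minimum through an evaluation at or after 4 months. Add the Measurement Form to event monitoring.
2. **Success definition (16.31).** Require for success a tumor evaluation at or after 4 months, within a stated window, that shows no progression. The 8-weekly schedule falls at weeks 16 and 24, and 16.13 equates 4 months with 16 weeks, so the window should say which evaluation counts. State that death before 4 months is a failure. Report a sensitivity analysis that counts patients without such an evaluation as failures.
3. **Censoring (16.52, 17.3), secondary.** Censor PFS at the last adequate tumor evaluation, broadly as 16.52 already does for duration of response.

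The sample size and the 17-of-37 rule do not change. The cost is protocol and SAP wording, one added form in event monitoring, and a few additional scans. Section 19.0 does not list tumor imaging among the research-funded items, so funding for those scans needs to be settled.

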19.0 Budget

- 19.1 Costs charged to patient: Routine clinical care will be the responsibility of the patient and or their insurance carrier.
- 19.2 Items to be research funded: Serum gold levels; Sirolimus; Auranofin; Lipid Panel at Baseline, C2, C3, and C4; Research blood draw and tissue collection and processing.
- 19.3 Other budget concerns: None

Appendix I: ECOG PERFORMANCE STATUS

Grade

- Fully active, able to carry on all pre-disease activities without restriction (Karnofsky 90 100).
- Restricted in physically strenuous activity but ambulatory and able to carry out work of a light or sedentary nature, e.g., light housework, office work (Karnofsky 70-80).
- Ambulatory and capable of all self-care, but unable to carry out any work activities. Up and about more than 50 percent of waking hours (Karnofsky 50-60).
- 3 Capable of only limited self-care, confined to bed or chair 50 percent or more of waking hours (Karnofsky 30-40).
- 4 Completely disabled. Cannot carry on any self-care. Totally confined to bed or chair (Karnofsky 10-20).
- 5 Dead

Appendix II: PATIENT'S MEDICATION DIARY

| Today's date | | |   | | | | | |
|--|---|-----------------|---------------------|------------------|--------------|----------------|----------|--|
| | | | acceptable) | Patient Study ID | | | | |
| | | (initials | acceptable) | | | | | |
| 1. C 2. Y pr 3. R | omplete ou will efer. ecord th | ne date, the nu | | when you to | ok them | | | |
| Date | Day | Comments | | | | | | |
| | 1 | taken | | | 17 | taken | | |
| | 2 | | | | 18 | | | |
| | 3 | | | | 19 | | | |
| | 4 | | | | 20 | | | |
| | 5 | | | | 21 | | | |
| | 6 | | | | 22 | | | |
| | 7 | | | | 23 | | | |
| | 8 | | | | 24 | | | |
| | 9 | | | | 25 | | | |
| | 10 | | | | 26 | | | |
| | 11 | | | | 27 | | | |
| | 12 | | | | 28 | | | |
| | 13 | | | | 29 | | | |
| | 14 | | | | 30 | | | |
| | 15 | | | | 31 | | | |
| | 16 | | | • | | | | |
| Physicia | an's Of | fice will comp | olete this section: | | | Date: | | |
| 1. D | ate pation | ent started pro | tocol treatment | Date | patient | was removed fr | om study | |
| 2. Patient's planned daily dose Total number of pills taken this month | | | | | n this month | | | |
| Physic | cian/Nu | rse/Data Mana | nger's Signature | | | | | |

Appendix III: Percent of Normal Bone Marrow Irradiated using Standard Radiation Ports*

| | Marrow Volume At Risk |
|---|--------------------------|
| | 7 KI KISK |
| Skull (not including mandible) | 12% |
| Upper limb girdle (unilateral) | 4% |
| (humeral head, scapulae, clavicle) | |
| Sternum | 2% |
| Ribs (all) | 8% |
| Ribs (hemithorax) | 4% |
| Cervical vertebrae (all) | 3% |
| Thoracic vertebrae (all) | 14% |
| Lumbar vertebrae (all) | 11% |
| Sacrum | 14% |
| Pelvis (including both innominates and both femoral | 26% |
| heads and necks) | |
| Mantle (approximate) | 25% |
| Upper para aortic nodes (approximate) | 11% |
| Inverted Y (approximate) | 45% |

^{*}Based on Ellis RE: Phys Med Biol 5:255, 1961

